15.0 Drug Information

15.1 Pembrolizumab (MK-3475, SCH 900475, Keytruda®)

15.11 **Background:** Pembrolizumab is a potent humanized IgG4 monoclonal antibody with high specificity of binding to the PD-1 receptor, thus inhibiting its interaction with PD-L1 and PD-L2. Based on preclinical *in vitro* data, pembrolizumab has high affinity and potent receptor blocking activity for PD-1.

15.12 **Formulation:**

Pembrolizumab (MK-3475) Solution for Infusion is a sterile, non-pyrogenic aqueous solution supplied in single-use Type I glass vial containing 100 mg/4 mL of pembrolizumab (MK-3475). The product is preservative-free solution which is essentially free of extraneous particulates. s available as a liquid 25 mg/mL, 100 mg/vial.

15.13 **Preparation and storage:**

Vials should be stored in the refrigerator at temperatures between 2-8°C.

Drug concentrate is further diluted with normal saline (or 5% dextrose) in the concentration range of 1 to 10 mg/m in IV containers made of polyvinyl chloride (PVC) or non-PVC material. Reconstituted vials should be immediately used to prepare the infusion solution in the IV bag and the infusion solution should be immediately administered. Diluted pembrolizumab solutions may be stored at room temperature for a cumulative period of up to 4 hours. This includes room temperature storage of admixture solutions in the IV bags and the duration of infusion. In addition, IV bags can be stored at 2-8 °C for up to a cumulative time of 20 hours.

15.14 **Administration:**

Pembrolizumab is administered by intravenous infusion over 30 minutes via a 0.22 micron in-line filter. The final infusion volume must be between 1 and 10 mg/mL. Maximum rate of infusion should not exceed 6.7 mL/minute through a peripheral or indwelling catheter. Flush the line with 0.9% NaCL following the completion of the infusion.

15.15 **Pharmacokinetic information:**

- a) Absorption – Steady-state is predicted to be achieved after ~18 weeks of repeated dosing, with ~2.2-fold accumulation in exposure during administration Q3W relative to exposure observed following single dose administration. The majority (~81%) of this accumulation has occurred by the fourth dose. In the dose range studied for efficacy (2 to 10 mg/kg), pembrolizumab exposure increases in a dose-proportional manner, with clearance being independent of time or pembrolizumab concentration.
- b) Distribution – Pembrolizumab has a limited volume of distribution.
- c) Excretion – The systemic clearance of pembrolizumab is ~0.22 L/day and the terminal elimination half-life ($t_{1/2}$) is estimated to be ~26 days.
- d) Metabolism - Pembrolizumab is catabolized by general protein degradation processes; typical small molecule metabolic pathways (eg, cytochrome P450 enzymes, glucuronosyltransferases) do not contribute to its clearance.

15.16 **Potential Drug Interactions:** There are no known significant drug interactions.

15.17 **Known potential toxicities:**

Common known potential toxicities, > 10%:

Dermatologic: Pruritus, skin rash
 Gastrointestinal: diarrhea
 Neuromuscular & skeletal: arthralgia, back pain
 Respiratory: Cough

Less common known potential toxicities, 1% - 10%:

Infusion related reactions
 Dermatologic: vitiligo, severe skin reactions
 Endocrine & metabolic: Hypothyroidism, hyperthyroidism, hyponatremia
 Gastrointestinal: Colitis, abdominal pain
 Respiratory: Pneumonitis

Rare known potential toxicities, <1% (Limited to important or life-threatening):

Secondary adrenocortical insufficiency (immune-mediated), hepatitis (including autoimmune hepatitis), hypophysitis, nephritis, Guillain-Barre syndrome (immune-mediated), myositis (immune-mediated), pancreatitis (immune-mediated), uveitis (immune-mediated), and Type 1 diabetes mellitus.

Stevens-Johnson syndrome, Toxic Epidermal Necrolysis, and Immune-mediated myocarditis

Two important potential risks have been identified, although the data available thus far for these events does not provide sufficient evidence of a causal relationship to pembrolizumab. The two important potential risks are: a) myasthenic syndrome, and b) an increased risk of severe complications (such as early severe graft versus host disease and venoocclusive disease) of allogeneic transplant in patients with hematologic malignancies who have previously been treated with PD-1 inhibitors. The Sponsor continues to monitor and collect data on these potential risks in order to further characterize their potential relationship to Pembrolizumab.

15.18 **Drug procurement:** Pembrolizumab will be provided free of charge to study participants by Merck.

15.19 **Nursing Guidelines:**

- 15.191 Pembrolizumab side effects vary greatly from those of traditional chemotherapy and can vary in severity from mild to life threatening. Instruct patients to report any side effects to the study team immediately. Side effects may be immediate or delayed up to months after discontinuation of therapy. Most side effects are reversible with prompt intervention of corticosteroids.
- 15.192 Diarrhea can be seen however is less common than that seen with anti-CTLA-4 agents. However it can be severe, leading to colonic perforation. Instruct patients to report ANY increase in the number of stools and/or change in baseline, blood in the stool, abdominal pain to the study team immediately.
- 15.193 Rash/pruiritis/dermatitis is seen. Patients should report any rash to the study team. Treat per [Section 9.0](#) and monitor for effectiveness.

- 15.194 Monitor LFT's closely as elevations in these levels could indicate early onset autoimmune hepatitis. Patients should also be instructed to report any jaundice, or right upper quadrant pain to the study team immediately.
 - 15.195 Pneumonitis can be seen and may be mild (only seen on imaging) to severe. Patients should be instructed to report any SOB, dyspnea, cough, chest pain, etc. to the study team immediately. Patients reporting these symptoms should have a pulse ox checked and consider immediate imaging per the treating MD.
 - 15.196 Endocrinopathies (including hypopituitarism, hypothyroidism, hypophysitis, and adrenal insufficiency) are seen with this agent. Patients may present only with the vague sense of fatigue and "not feeling well". Additional symptoms may be that of nausea, sweating and decreased activity tolerance. Instruct patients to report these signs or symptoms immediately and obtain appropriate labs as ordered by MD.
 - 15.197 Patients who are started on steroid therapy for any side effects of pembrolizumab toxicity should be instructed to take the steroids as ordered, and not to discontinue abruptly as symptoms may return and be severe. Patients may be on steroid therapy for weeks. Instruct patients to report any increase or change in side effects with any dosage decrease as patients may need a slower taper.
 - 15.198 Fatigue is common and may or may not be associated with immune related side effects. Assess patient's fatigue level prior to each cycle of therapy and report any *changes to the study team*.
 - 15.199a Patients should avoid receiving live vaccines within 30 days of study drug administration or per other study guidelines.
 - 15.199b Patients who have undergone an allogenic bone marrow transplant, have an increased risk of severe complications including early GVHD, and venoocclusive disease, if they have previously been treated with Pembrolizumab.
- 15.2 Lenalidomide (Revlimid®, CC-5013, CDC-501)
- 15.21 **Background:** Lenalidomide has a wide range of effects, including the inhibition of hematopoietic tumor cell proliferation, the enhancement of T cells and natural killer (NK) cell activity, the modulation of stem cell differentiation, the inhibition of angiogenesis, and the inhibition of inflammation.
 - 15.22 **Formulation:** For clinical study, lenalidomide is provided as 1.25-, 2.5-, 5-, 10-, 15-, 20-, and 25-mg capsules for oral administration. Each capsule contains lenalidomide as the active ingredient and the following inactive ingredients: anhydrous lactose, microcrystalline cellulose, croscarmellose sodium, and magnesium stearate. The lenalidomide capsules are supplied in push-through blister foil or tamper-evident, child-resistant, opaque, high-density polyethylene (HDPE) containers with HDPE caps.
 - 15.23 **Preparation and storage:** Lenalidomide should be stored at room temperature, between 59 and 86°F (15-30°C). Store drug away from direct sunlight.

15.24 **Administration:** Capsules are administered by mouth daily with water. Patients should not break, chew or open the capsules.

15.25 **Pharmacokinetic information:**

a) Absorption – Lenalidomide is rapidly absorbed following oral administration to healthy subjects, with maximum plasma concentrations occurring between 0.5 and 1.5 hours post-dose. Co administration with a high-fat and high-calorie meal in healthy subjects reduced the extent of absorption, resulting in an approximately 20% decrease in AUC and 50% decrease in C_{max} in plasma.

In the pivotal MM and MDS registration trials where the efficacy and safety were established for lenalidomide, the drug was administered without regard to food intake. Thus, lenalidomide can be administered with or without food.

Multiple dosing (up to 100 mg BID) did not cause marked drug accumulation. In plasma, the relative exposures of the S- and R-enantiomers of lenalidomide are approximately 55% and 45% respectively.

b) Distribution – In vitro (14C)-lenalidomide binding to plasma proteins was low, with mean plasma protein binding at 22.7% and 29.2% in multiple myeloma subjects and healthy volunteers, respectively. In a multiple dose study in healthy subjects administered 25 mg/day for 4 days, a small amount of lenalidomide (<0.01% of the dose) was detected in semen. Three days after stopping the drug, the amount of drug in semen was undetectable.

c) Metabolism – Results from in vitro metabolism studies showed that lenalidomide was neither metabolized by nor inhibited or induced the CYP pathway. In healthy subjects, lenalidomide undergoes limited metabolism and the parent compound is the predominant circulating component.

d) Excretion – Approximately 65% to 85% of lenalidomide is eliminated unchanged through urinary excretion in subjects with normal renal function. The half-life of elimination is approximately 3 to 4 hours at the clinically relevant doses (5 to 50 mg/day). Steady-state levels are achieved within 4 days.

Analyses in subjects with impaired renal function indicate that as renal function decreases, the total drug clearance decreases proportionally resulting in an increase in AUC. The t_{1/2} of lenalidomide was longer by approximately 6 to 12 hours in subjects with moderate or worse RI.

15.26 **Potential Drug Interactions:**

Results from human in vitro metabolism studies indicated that lenalidomide is not metabolized by CYP enzymes, suggesting that administration of lenalidomide with drugs that inhibit CYP enzymes is not likely to result in metabolic drug interactions. Lenalidomide did not inhibit or induce marker enzyme activities for human CYP1A2, 2C9, 2C19, 2D6, 2E1, or 3A4 in vitro. In cultured human hepatocytes, lenalidomide did not induce the catalytic activities of CYP1A2, 2B6, 2C9, 2C19, or 3A4/5. Results from in vitro studies showed that lenalidomide is not a substrate of human MRP1, MRP2, or MRP3 efflux transporters. Results from in vitro studies also demonstrated that lenalidomide is not a substrate of human OAT1, OAT3, OATP1B1 (OATP2), nor OCT1. Lenalidomide is a weak substrate of P-glycoprotein, but does not inhibit P-glycoprotein. Therefore, clinically relevant drug-drug interactions are unlikely between lenalidomide and P-glycoprotein substrates or inhibitors.

Co-administration of multiple doses of 10 mg of lenalidomide had no effect on the single dose pharmacokinetics of R- and S-warfarin. Co-administration of

single 25-mg dose warfarin had no effect on the pharmacokinetics of lenalidomide. However, it is not known whether there is an interaction during clinical use.

Concomitant administration with lenalidomide 10 mg/day increased the plasma exposure of digoxin (0.5 mg, single dose) by 14%. It is not known whether the effect will be different in the therapeutic situation (higher lenalidomide doses and concomitant treatment with dexamethasone).

15.27 **Known potential toxicities:**

Pregnancy Warning: Lenalidomide is structurally related to thalidomide, a known human teratogen. Therefore, in an effort to prevent to the greatest extent possible any chance of fetal exposure, lenalidomide is available through a controlled distribution program, specifically a pregnancy prevention program called Revlimid REMS. It is contraindicated in women who are or may become pregnant. Female subjects of childbearing potential are required to submit to regular pregnancy testing, and to agree to use effective forms of birth control as outlined in study protocols. Male subjects, even those who have had a vasectomy, must agree to use a condom during sexual contact with a pregnant woman or a woman who can become pregnant.

Very Common AEs (≥10%): anemia, febrile neutropenia, leukopenia, neutropenia, thrombocytopenia, cataracts, blurred vision, abdominal pain, constipation, diarrhea, dyspepsia, nausea, vomiting, asthenia, chills, edema including peripheral, fatigue, pyrexia, abnormal liver function tests, bacterial, viral and fungal infections (including opportunistic infections), bronchitis, nasopharyngitis, sinusitis, pneumonia, rhinitis, upper respiratory tract infection, urinary tract infection weight decreased, decreased appetite, hyperglycemia, hypocalcemia, hypokalemia, arthralgia, back pain, bone pain, muscle spasms, musculoskeletal pain, myalgia, pain in extremity, dizziness, dysgeusia, headache, hypoesthesia, neuropathy peripheral, neuropathy, tremor, depression, insomnia, renal failure, cough, dyspnea, epistaxis, pharyngitis, pulmonary embolism, dry skin, pruritus, rash, and deep vein thrombosis.

Common (≥1% and <10%): granulocytopenia, hemolytic anemia, lymphopenia, pancytopenia, acute myocardial infarction, atrial fibrillation, cardiac failure, congestive heart failure, myocardial ischemia, tachycardia, vertigo, upper abdominal pain, dry mouth, toothache, chest pain, fall, cholestasis, bacteremia, cellulitis, erysipelas, gastroenteritis, herpes simplex, herpes zoster, influenza, lower respiratory infection, respiratory infection, sepsis, contusion, alanine aminotransferase increased, c-reactive protein increased, gamma-glutamyltransferase increased, dehydration, diabetes mellitus, gout, hypercalcemia, hyperuricemia, hypophosphatemia, hypomagnesemia, hyponatremia, iron overload, muscular weakness, acute myeloid leukemia, basal cell carcinoma, Myelodysplastic syndrome, squamous cell carcinoma of skin, T-cell type acute leukemia, tumor flare, tumor lysis syndrome, cerebrovascular accident, lethargy, paresthesia, peripheral sensory neuropathy, syncope, mood altered, renal failure, respiratory distress, erythema, hyperhidrosis, night sweats, hematoma, hypertension, hypotension, peripheral ischemia, thrombosis, and vasculitis.

Uncommon, limited to important or life-threatening (<1%): hypersensitivity, Graft vs. Host Disease, viral reactivation (such as hepatitis B virus or herpes zoster), DRESS.

The following additional adverse reactions have been reported in Celgene-sponsored clinical studies and are considered by the company to be possibly related to the administration of lenalidomide: granulocytopenia, cataract, vision blurred, abdominal pain upper, dry mouth, gastrointestinal motility disorder, toothache, fall, herpes simplex, influenza, rhinitis, hyperuricemia, hypophosphatemia, iron overload, musculoskeletal pain, dysgeusia, headache, paresthesia, dry skin, hyperhidrosis, and pruritus.

Please refer to the Investigator Brochure for a more comprehensive list of treatment-emergent adverse events.

15.28 **Drug procurement and accountability:**

As a requirement of the REMS program, access to Lenalidomide is restricted. Lenalidomide is approved for marketing only under a FDA approved, restricted distribution program called REVLIMID REMS (www.REVLIMIDREMS.com) formerly known as the RevAssist program. Physicians, pharmacies, and patients must be registered; a maximum 28-day supply may be dispensed; a new prescription is required each time it is filled; pregnancy testing is required for females of childbearing potential.

Drug will be shipped directly to the patient through Revlimid REMS Program. Any unused lenalidomide should be returned for disposition in accordance with the REVLIMID REMS™ program.

15.29 **Nursing Guidelines**

15.291 The most common side effects are neutropenia and thrombocytopenia.

15.292 Due to the highly teratogenic potential of the closely related thalidomide, it is highly recommended that all women of childbearing age group and all men use effective contraception during therapy. All staff who are pregnant or who can become pregnant should not handle this drug outside of its original packaging.

15.293 Instruct patient to report any rash immediately to the study team.

15.294 Lenalidomide capsules should be swallowed whole, and should not be broken, chewed or opened.

15.295 If a dose of lenalidomide is missed, it should be taken as soon as possible on the same day. If it is missed for the entire day, it should not be made up.

15.296 Patients who take more than the prescribed dose of lenalidomide should be instructed to seek emergency medical care if needed and contact study staff immediately.

15.3 **Dexamethasone for Oral Administration (DXM)**

15.31 **Background:** Dexamethasone is an adrenal corticosteroid compound. Dexamethasone decreases inflammation by suppression of neutrophil migration, decreased production of inflammatory mediators, and reversal of increased capillary permeability; suppresses normal immune response. Dexamethasone's mechanism of antiemetic activity is unknown.

15.32 **Formulation:** Commercially available for oral administration as:
Tablets [scored]: 0.5 mg, 0.75 mg, 1 mg, 1.5 mg, 2 mg, 4 mg, and 6 mg.

Solution, oral: 0.5 mg/mL (500 mL).

Solution, oral concentrate: Dexamethasone Intensol: 1 mg/mL (30 mL).

- 15.33 **Preparation, storage, and stability:** Refer to package insert for complete preparation and dispensing instructions. Store oral tablets at room temperature between 20°C to 25°C (60°F to 77°F). Protect from moisture. Dispense in a well-closed, light-resistant container as defined in the USP/NF. Store oral liquid at room temperature, do not freeze. Do not use if solution contains a precipitate. Refer to commercial package for drug expiration date.
- 15.34 **Administration:** Refer to the treatment section for specific administration instructions. May be taken with meals to decrease GI upset.
- 15.35 **Pharmacokinetic information:**
Onset of action: Prompt
Duration of metabolic effect: 72 hours
Metabolism: Hepatic
Half-life elimination: Normal renal function: 1.8-3.5 hours; **Biological half-life:** 36-54 hours
Time to peak, serum: Oral: 1-2 hours
Excretion: Urine and feces
- 15.36 **Potential Drug Interactions:**
Cytochrome P450 Effect: Substrate of CYP3A4 (major); **Induces** CYP2A6 (weak), 2B6 (weak), 2C8 (weak), 2C9 (weak), 3A4 (strong)
Increased Effect/Toxicity: Aprepitant, azole antifungals, calcium channel blockers, cyclosporine, estrogens, and macrolides may increase the serum levels of corticosteroids. Corticosteroids may increase the hypokalemic effects of amphotericin B or potassium-wasting diuretics (loop or thiazide); monitor. Refer to the package insert for a listing of other drugs.
Decreased Effect: Antacids and bile acid sequestrants may reduce the absorption of corticosteroids; may reduce the absorption of corticosteroids; separate administration by 2 hours. Aminoglutethimide, barbiturates, and CYP3A4 inducers may reduce the serum levels/effects of dexamethasone and dexamethasone may decrease the levels/effects of other CYP3A4 substrates. Serum concentrations of isoniazid may be decreased by corticosteroids. Corticosteroids may lead to a reduction in warfarin effect. Corticosteroids may suppress the response to vaccinations.
Ethanol/Nutrition/Herb Interactions:
Ethanol: Avoid ethanol (may enhance gastric mucosal irritation).
Food: Dexamethasone interferes with calcium absorption. Limit caffeine.
Herb/Nutraceutical: Avoid cat's claw (*Uncaria tomentosa*), echinacea (have immunostimulant properties)
- 15.37 **Known potential adverse events:** Consult the package insert for the most current and complete information.
Common known potential toxicities, frequency not defined:
Fluid and electrolyte disturbances, congestive heart failure in susceptible persons, hypertension, euphoria, personality changes, insomnia, exacerbation of infection, exacerbation or symptoms of diabetes, psychosis, muscle weakness, osteoporosis, vertebral compression fractures, pancreatitis, esophagitis, peptic ulcer, dermatologic disturbances,

convulsions, vertigo and headache, endocrine abnormalities, ophthalmic changes, and metabolic changes. Some patients have experienced itching and other allergic, anaphylactic or hypersensitivity reactions. Withdrawal from prolonged therapy may result in symptoms including fever, myalgia and arthralgia.

- 15.38 **Drug procurement:** Commercial supplies. Pharmacies or clinics shall obtain supplies from normal commercial supply chain or wholesaler.
- 15.39 Nursing Guidelines:
- 15.391 Monitor patient regularly for hypertension, CHF and other evidence of fluid retention.
 - 15.392 Advise patient of possible mood or behavioral changes, i.e., depression, euphoria, insomnia, even psychosis. Instruct patient to report any suspected changes to healthcare team.
 - 15.393 Assess for symptoms of gastric ulcer, heartburn, or gastritis. Suggest antacids. Instruct patient to report symptoms to healthcare team if unable to control.
 - 15.394 Evaluate signs of infection, particularly local candidal infections and treat appropriately.
 - 15.395 Monitor blood glucose frequently.
 - 15.396 Instruct patient to report frequent, unrelenting headaches or visual changes to healthcare team.
 - 15.397 Advise patient that easy bruising is a side effect.

16.0 Statistical Considerations and Methodology

16.1 Overview

This is a phase II study of a novel regimen of pembrolizumab with lenalidomide and dexamethasone for initial treatment of newly diagnosed multiple myeloma patients requiring therapy. This study is designed to assess the VGPR or better response rate associated with therapy with pembrolizumab added to standard doses of lenalidomide and dexamethasone, in patients with previously untreated multiple myeloma using a single stage phase II study design with an interim analysis.

- 16.11 **Endpoint:** The primary endpoint of the trial is the rate of complete or very good partial response after 4 cycles of induction treatment. A success will be defined as an sCR, CR, or VGPR noted as the objective status on two consecutive evaluations. Response will be evaluated using the first 4 cycles of induction therapy. Throughout Section 16.0, sCR, CR, or VGPR will be considered synonymous with “success” in the phase II portion, unless specified otherwise.
- 16.12 **Sample Size:** The single-stage study design with an interim analysis to be used is fully described below. A minimum of 13 and a maximum of 37 evaluable patients will be accrued in the phase II study unless undue toxicity is encountered. We anticipate accruing an additional 4 patients to account for ineligibility, cancellation, major treatment violation, or other reasons for a maximum of 41 patients.
- 16.13 **Accrual Rate and Study Duration:** The anticipated accrual rate is 2-3 evaluable multiple myeloma patients per month. At this rate, it will likely take about 1.5 years to enroll the patients. The maximum total study duration is expected to be approximately 2 years, or until the last patient accrued has been observed for at least 6 months.

16.2 Statistical Design:

16.21 Decision Rule:

A combination of lenalidomide plus dexamethasone, an oral regimen, is the mainstay therapy for newly diagnosed multiple myeloma. In a large multi-center study, 208 patients were evaluated for response to treatment with lenalidomide plus low dose dexamethasone.⁶ Forty-nine patients (24%) achieved a complete or very good partial response. An increase in the rate of complete plus very good partial response with the addition of pembrolizumab to lenalidomide plus dexamethasone would be of interest.

The largest success proportion where the proposed treatment regimen would be considered ineffective in this population is 25%, and the smallest success proportion that would warrant subsequent studies with the proposed regimen in this patient population is 45%. The following one-stage design with an interim analysis is based on a Simon optimum design¹³ and requires 37 evaluable patients to test the null hypothesis that the true success proportion in this patient population is at most 25%.

- 16.211 **Interim Analysis:** Enter 13 evaluable patients into the study. If 3 or fewer successes are observed in the first 13 evaluable patients, we will consider this regimen ineffective in this patient population and terminate this study. Otherwise, if the number of successes is at least 4, we will continue accrual.

- 16.212 Final Decision Rule: Enter an additional 24 evaluable patients into the study. If 12 or fewer successes are observed in the first 37 evaluable patients, we will consider this regimen ineffective in this patient population. Otherwise, if the number of successes is at least 13, this will be considered evidence of promising activity and the treatment may be recommended for further testing in subsequent studies.
- 16.213 Over Accrual: If more than the target number of patients are accrued, the additional patients will not be used to evaluate the stopping rule or used in any decision making process. Analyses involving over accrued patients are discussed in Section 16.34.
- 16.214 NOTE: We will not suspend accrual at the interim analysis to allow the first 13 patients to become evaluable, unless undue toxicity is observed. Given the limited overall sample size and the inclusion of an adverse events stopping rule, we feel it is ethical to not halt accrual for the interim analysis. However, if accrual is extremely rapid, we may temporarily suspend accrual in order to obtain safety data on these patients before re-opening accrual to further patients
- 16.22 Power and Significance Level: Assuming that the number of successes is binomially distributed, the significance level is .09, i.e. there is a 9% chance of finding the drug to be effective when it truly is not. The probability of declaring that this regimen warrants further study (i.e. statistical power) and the probability of stopping after the interim analysis under various success proportions can be tabulated as a function of the true success proportion as shown in the following table.

If the true success proportion is..	0.25	0.30	0.35	0.40	0.45
Then the probability of declaring that the regimen warrants further study is...	0.092	0.256	0.485	0.703	0.856
And the probability of stopping after the interim analysis is ...	0.584	0.421	0.278	0.169	0.093

- 16.23 Other considerations: Adverse events, quality/duration of response, and patterns of treatment failure observed in this study, as well as scientific discoveries or changes in standard care will be taken into account in any decision to terminate the study.

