7.0 Protocol Treatment

7.1 Treatment Schedule

Cycle length: 28 days.

Agent	Route	Dose	Day	Retreatment
Lenalidomide	PO	25 mg*	1-21	Every 28 days
Pembrolizumab	IV	200mg	Every 21 days	Every 21 days
Dexamethasone	PO	40 mg	1, 8, 15, 22	Every 28 days

* If the patient has renal insufficiency, lenalidomide dose modifications should be made according to the following criteria:

CrCl >50 mL/min: No adjustment

CrCl 30-50 mL/min: 10 mg/day

CrCl <30 mL/min (no dialysis): 15 mg every 48 hours

CrCl <30 mL/min (dialysis): 5 mg daily (after HD (hemodialysis) on HD days)

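### Section 16.12 gives 13 as the minimum accrual, but with accrual left open it is only the interim decision size: about 20 to 24 evaluable patients will have entered when the 13th outcome is known

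*Combined protocol and SAP*

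**What the plan says.** All references are to the combined protocol and SAP.

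- **Size (16.12).** "A minimum of 13 and a maximum of 37 evaluable patients will be accrued in the phase II study", with a proviso for undue toxicity. Four more patients are allowed for non-evaluability, giving a maximum of 41.
- **Interim rule (16.211).** With 3 or fewer successes among the first 13 evaluable patients the study terminates; with at least 4 it goes on to 37. Section 16.21 describes this as a one-stage design with an interim analysis, based on a Simon optimum design.
- **Accrual at the interim (16.214).** "We will not suspend accrual at the interim analysis to allow the first 13 patients to become evaluable". The exception is undue toxicity. A temporary pause is also possible if accrual is extremely rapid. The section argues that not halting is ethical, given the small trial and the adverse-event stopping rule.
- **Accrual rate (16.13).** "The anticipated accrual rate is 2-3 evaluable multiple myeloma patients per month". Enrolment is expected to take about 1.5 years.
- **Endpoint (16.11, 7.1).** "Response will be evaluated using the first 4 cycles of induction therapy", and "Cycle length: 28 days". In addition, "A success will be defined as an sCR, CR, or VGPR noted as the objective status on two consecutive evaluations".
- **Overrun (16.213, 16.34).** Patients beyond a target number are kept out of the stopping rule and all decisions, but enter the final estimates and confidence intervals.

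**The concern.** The smallest trial size in 16.12 is the first-stage size of a design that waits for its interim result, whereas 16.214 describes a trial that does not wait. Patients who enter during the wait are evaluable under 16.311 once they begin treatment, unless ineligible or a major violation, so they count towards the quantity that 16.12 describes. The plan nowhere estimates how many there will be.

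What is at stake is exposure and the benefit of the early look, not the validity of the test. Someone judging how many patients would be treated if the combination adds nothing would take 13 from 16.12. There is also a small reporting gap: the target number in 16.213 is not tied to 13 or to 37, so at an interim stop the plan does not clearly say which patients are overrun.

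**Working it through.** **1. The plan's own figures reproduce.** With X1 ~ Bin(13, p) and X2 ~ Bin(24, p):

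- P(stop) = P(X1 ≤ 3)
- P(declare promising) = Σ over x = 4 to 13 of P(X1 = x) · P(X2 ≥ 13 − x)

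At p = 0.25 these give 0.5843 and 0.0920 (plan: 0.584 and 0.092). At p = 0.45 they give 0.0929 and 0.8560 (plan: 0.093 and 0.856). The intermediate columns of the table in 16.22 also agree.

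**2. Time to the 13th outcome.** Four cycles are 4 × 28 = 112 days, and 112 / 30.44 = 3.68 months. If confirmation is assumed to need one further cycle, this becomes 140 days, or 4.60 months. The documents do not say whether confirmation may fall after cycle 4, so the second figure is an assumption.

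**3. Patients entered by then.** Entered = 13 + rate × months. The 1.5-year enrolment period implies 37 / 18 = 2.06 evaluable patients per month, so that rate is shown too. Expected N at p = 0.25 is 0.584 × entered + 0.416 × 37. A stop at 13 would spare 37 − 13 = 24 patients, so the share of the saving lost is (entered − 13) / 24.

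| Wait | Rate per month | Entered | Expected N | Saving lost |
|---|---|---|---|---|
| 112 days | 2 | 20.4 | 27.3 | 7.4/24 = 31% |
| 112 days | 2.06 | 20.6 | 27.4 | 7.6/24 = 32% |
| 112 days | 3 | 24.0 | 29.4 | 11.0/24 = 46% |
| 140 days (assumed) | 2 | 22.2 | 28.4 | 9.2/24 = 38% |
| 140 days (assumed) | 3 | 26.8 | 31.0 | 13.8/24 = 57% |

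If accrual truly stopped at 13, expected N would be 0.584 × 13 + 0.416 × 37 = 23.0.

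**4. How likely is a stop with only 13 entered?** Taking accrual as a Poisson process (an assumption), the chance that nobody enters during the 112-day wait is exp(−7.36) = 0.06% at 2 per month, and smaller at 3 per month. For the mean overrun to be below one patient, accrual would have to be below 1 / 3.68 = 0.27 per month.

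**5. Acting as soon as futility is certain.** Ten failures among the first 13 is the same event as 3 or fewer successes. If outcomes become known in order of entry, with s successes in total, the number of patients remaining after the 10th failure averages (3 − s) + s(4 − s)/(14 − s): 3, 2.23, 1.33 and 0.27 for s = 0, 1, 2, 3. The binomial probabilities at p = 0.25 are 0.0238, 0.1029, 0.2059 and 0.2517. The average given a stop is therefore (0.0713 + 0.2296 + 0.2745 + 0.0686) / 0.5843 = 1.10 patients spared. A simulation that assumes 30% of failures are already known after 2 cycles gives up to about 1.6. Even then, stopping with only 13 entered has a chance of about 3% or less (about 1.5% or less without early-known failures).

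**The case against.** The strongest reply is that this is a disclosed choice. Section 16.214 says accrual will not pause and gives its reasons. The plan quotes no expected sample size, so 23.0 is a benchmark supplied by this review. Every operating characteristic the plan does quote is correct. Sections 16.213 and 16.34 already cover most of the overrun handling. All of that stands, and it makes this a point about wording and not about validity.

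Four stronger readings are tempting, but the documents do not support them.

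- *A trial of 13 is impossible.* Thirteen remains a literal lower bound. A toxicity halt, a pause for rapid accrual, slow accrual or futility that becomes certain early could leave the total at or near it.
- *The early-stopping protection is largely lost.* Without the assumed extra cycle, 54% to 69% of the 24-patient saving is kept. Less than half is kept only at 3 per month with that extra cycle.
- *More patients would be treated than the plan states.* Twenty to 27 lies inside the stated range of 13 to 37.
- *The error rates are affected.* Decisions use only the first 13 and the first 37 evaluable patients, so they are not.

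The upper figures also deserve caution: 1.5 years of enrolment points to the low end of the accrual range, hence about 20 to 21 patients. What the reply does not answer is that 16.12 still presents 13 as the minimum accrual, with no estimate anywhere of the overrun that 16.214 creates.

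**Conclusion.** The point holds as a mismatch between 16.12 and 16.214. Thirteen is the interim decision size; under the planned conduct a futility stop there will almost never happen. About 20 to 24 evaluable patients will have entered when the 13th outcome is known, and about 20 to 21 at the rate implied by 1.5 years of enrolment. The figure reaches about 27 only at 3 per month with one further confirmation cycle.

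Expected sample size at a 25% success rate is about 27 to 29 (up to 31), not 23.0, and about a third to just under half of the saving from a futility stop is lost. These figures rest on steady accrual at the stated rate, no pause, and a wait of four full cycles for the 13th patient. The plan's inference is sound as written.

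**What to change.** Three wording changes.

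1. **16.12:** describe 13 as the interim decision size and add that about 20 to 24 evaluable patients (up to 27 if confirmation runs one cycle longer) are expected to have entered by then.
2. **16.213:** tie the target number to 13 when the trial stops at the interim, so that later entrants stay out of the decision and are reported under 16.34.
3. **16.211:** apply the futility rule as soon as 10 of the first 13 evaluable patients are known failures. This is the same rule with the same error rates, and it spares about 1 to 1.6 patients on average at a stop. No matching rule for passing at the 4th success is needed, because accrual is not paused in any case.

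The cost is a protocol wording change and a stated minimum that looks less favourable. Sample size, decision boundaries and the choice not to pause can all stay as they are.
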